9.2. Notification and Documentation of Adverse Events

AEs will be collected by the sponsor up to 30 days after administration of the last dose of study treatment.

All AEs must be recorded in the source document and in the CRD using medical terminology. Investigators should assess the severity (grade) of the event according to NCI-CTC AE V 4.0, assign a relationship to the trial drug, and seek and obtain appropriate information to determine the outcome and to evaluate whether it meets the criteria for classification as AAG that requires immediate communication. The researcher must provide any information requested by the promoter, in addition to that collected in the CRD.

All SAEs (as defined above) that occur during the clinical trial or within 30 days after the last dose of the study medication, regardless of the treatment group or the suspected relationship with the study treatment, must be reported by the investigator. Additionally, any SAEs that occur as a result of diagnostic procedures or interventions specific to this protocol must also be reported. Beyond this time period, only SAEs suspected to be related to the study drug should be reported.

Todos los Acontecimientos adversos graves deben ser reportados por FAX en las 24 h. posteriores de haber sido detectados a [REDACTED]

The AAG report must contain a complete written summary detailing the important aspects of the applicable adverse events. Where applicable, information about relevant medical records and autopsy reports should be included. Tracking information must be sent to MFAR, S.L. in the next 24 hours.

All SAEs suspected to be related to study treatment should be followed after withdrawal until the event or its sequelae have resolved or stabilized at a level acceptable to the investigator or designee.

9.3. Pregnancy notification

The pregnancy of a female patient or the partner of a male patient, not being a serious adverse event in itself, should also be managed expeditiously just like an SAE.

It must be registered on a specific pregnancy notification form, notified expeditiously (within 24 hours) from when it is known and followed until the end, even if a voluntary or spontaneous interruption occurs, describing the details of the birth and the presence or absence of any defect in the fetus or any congenital anomaly.

Potential effects of spermatogenesis: pregnancies that occur in the partner of a male patient must also be notified within 24 hours using the specific pregnancy form and followed until the end, even if a voluntary or spontaneous interruption occurs, describing the details of the pregnancy, birth and the presence or absence of any defect in the fetus or any congenital anomaly. Likewise, your pregnant partner would be instructed to contact his or her doctor immediately.

10. STATISTICAL CONSIDERATIONS

10.1. Study variables

Percentage of patients who have relapsed/not relapsed to the study treatment 6 months after starting it.

10.2. Primary objective

To determine whether palbociclib could delay disease progression in patients with anaplastic oligodendroglioma.

10.3. Hypothesis

Clinical basis: historical data for the elaboration of the study hypothesis have been obtained from the analysis of a database containing 350 patients with recurrent high-grade gliomas (125 anaplastic gliomas) who were prospectively treated in phase II studies. The 6-month progression-free survival (PFS-6m) was 31% for anaplastic gliomas (Wong et al. J Clin Oncol 17:2572-2578). The authors acknowledge the limitation because in this study the results were analyzed for all anaplastic gliomas and not only anaplastic oligodendrogliomas. However, no further published data are available regarding the results in recurrent anaplastic oligodendrogliomas.

Null hypothesis (H0): $P \leq P_0$

Alternative hypothesis to test (H1): $P \geq P_1$

Assumptions:

P: probability of remaining alive and progression-free at 6 months

P_0 : 25%

P_1 : 45%

Expected profit: 20% (25% vs. 45%)

Type I error, $\alpha \leq 0.05$

Type II error, $\beta \geq 0.20$

Sample size: 40 patients

A benefit will be considered if 18/40 patients are alive and progression-free at 6 months.

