4.2.4. Treatment of Anaplastic Oligodendrogloma

Regarding treatment, the first approach is surgical intervention. In this sense, retrospective studies as well as subgroup analyzes reach the same conclusion: a wide resection improves the patient's prognosis. Given the high possibility of tumor progression, in the 1980s radiotherapy was established as the standard of post-surgical treatment in high-grade gliomas.

In the 90s, studies were published that showed that they are chemosensitive tumors (PCV), unlike other brain tumors.¹² With these data, two studies were then designed, from which we have just obtained

results.^{13,14}: the RTOG 9402 study and the EORTC study 26951. In both cases, after an initial surgical approach, the question of whether chemotherapy (PCV: Procarbazine, CCNU and Vincristine) provided benefit to the radiotherapy treatment was attempted. , so the 2 randomized phase III studies were designed.

The primary endpoint in the EORTC study was PFS and OS. A total of 368 patients with oligodendroglial tumor were included between 1995 and 2002, aged between 16 and 70 years. The branches were well balanced for known prognostic factors. Adding PCV to radiotherapy increases median PFS from 13 to 24 months and OS from 31 to 42 months, statistically significantly. These results were further maintained when performing an analysis that included risk stratification by age, type of surgery, PS, and prior surgery for low-grade glioma.¹⁵ The next question he tried to answer is whether there is any way to identify those patients who will benefit the most. The results analyzed prospectively for 1p/19q, and retrospectively for MGMT and IDH, can help with this. 1p/19 was analyzed in 316 patients and 25% were co-deleted. MGMT was analyzed in 183 patients and 75% were methylated and IDH was analyzed in 176 patients and was mutated in 46%. For 1p/19 there is a benefit in PFS from 50 to 157 months and in OS from 9 years to a median not yet reached (>12 years) ($p=0.059$). However, in non-co-deleted patients, the differences do not reach statistical significance.

In 2012 we also learned the final results of the RTOG 9462 study, which were very similar to those of the EORTC study.¹⁶ Based on these data, post-surgical radiotherapy treatment will be complemented with chemotherapy in the event that there is loss of 1p/19q. In cases without chromosome loss, it is usual to use radiotherapy exclusively.

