6. PATIENT SELECTION CRITERIA

6.1. Inclusion criteria

1. Ability to understand and sign the informed consent document approved by the CEIC
2. Men or women aged ≥ 18 years.
3. Patients with anaplastic oligodendroglioma according to the new WHO (WHO) classification of 2016 (In Press)^{23,24,25} and confirmed histologically and molecularly at a central level. According to this classification, oligodendrogliomas must present mutations in IDH1/2 as well as a co-deletion of chromosomes 1p/19q.

USE: Patients with the initial diagnosis of grade 2 oligodendroglioma may be included as long as they have suffered a recurrence in which a new resection was performed whose diagnosis was grade 3.

USE 2: Patients previously diagnosed with Oligoastrocytoma grade 3 according to the WHO 2007 classification could be included if, in the centralized review, the criteria for Anaplastic Oligodendroglioma according to the new classification are met.

4. Patients in a relapse situation after having received radiotherapy and one or two lines of chemotherapy.

USE: Both previous radiotherapy and previous chemotherapy may have been received in an adjuvant situation or in previous recurrences. It is also admitted to have received concurrent chemoradiotherapy. In anaplastic oligodendrogliomas, patients have been able to receive chemotherapy or radiotherapy when they were still grade 2 tumors.

5. All patients must present positivity in the immunohistochemical study for the Rb protein in the tumor material analyzed by the central laboratory (Neuropathology Laboratory, Hospital Universitario 12 de Octubre).
6. Cases must have a paraffin-embedded tissue block available from a previous biopsy or surgery (previously archived tumor samples) for central histological and molecular determinations.
7. All patients must show disease progression on brain MRI as defined in the RANO Criteria.
8. Interval of at least one week between previous intracranial biopsy, adequately healed, and inclusion.
9. Interval of at least 12 weeks between previous radiotherapy and inclusion, unless:
 - a. Histopathological confirmation of recurrent tumor, the
 - b. Recurrence on MRI outside the radiotherapy field.
10. Patients must have recovered from prior therapies: 28 days from completion of any investigational compound and/or from completion of any cytotoxic treatment.
11. ECOG functional status ≤ 2 .
12. Stable or decreasing dose of corticosteroids during the five days prior to inclusion in the study.

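### Protocol 10.3: the null of 25%, the cited 31%, the 45% target and the 18/40 rule do not form one design, and power at 45% is 56%

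*Protocol*

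**What the plan says.** Protocol section 10.3 says its hypothesis rests on a database of 350 recurrent high-grade gliomas, 125 of them anaplastic. From it the section takes a single rate: "The 6-month progression-free survival (PFS-6m) was 31% for anaplastic gliomas". It warns that "the results were analyzed for all anaplastic gliomas and not only anaplastic oligodendrogliomas" and adds that "no further published data are available regarding the results in recurrent anaplastic oligodendrogliomas".

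The design lines follow:

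- P0 = 25% and P1 = 45%, with the difference presented as an expected gain of 20 points;
- type I error at most 0.05;
- type II error printed as at least 0.20;
- 40 patients.

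The section closes with the decision rule: "A benefit will be considered if 18/40 patients are alive and progression-free at 6 months".

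No sentence explains how 25% follows from 31%, and no test is named. The hypotheses are written in one direction (P at most P0 against P at least P1), but whether alpha is one-sided 5% or 2.5% is not said. Section 5 describes a single treatment arm. SAP section 1.2.1 names no reference rate for the 6-month estimate.

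**The concern.** In a single-arm trial the null rate is the comparator, and the cut-off decides what a positive result means. A reader of section 10.3 should be able to start from P0, P1, alpha and beta and arrive at N and the cut-off. Two things prevent this.

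First, the null lies six points below the only rate cited for it. The gain called 20 points is 45 − 31 = 14 points over that rate.

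Second, 18/40 is exactly 45%, the target rate itself. A rule that requires the observed rate to reach the target has only a little over an even chance of success when the target is true. If beta is read as 0.20, the protocol promises 80% power at 45% and the rule does not deliver it. A drug that met the sponsor's own target would fail this rule 44% of the time.

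**Working it through.** **Inputs, all from Protocol section 10.3.** Cited rate 31%; P0 = 25%; P1 = 45%; alpha 0.05; beta read as 0.20; N = 40; cut-off 18. The exact one-sided binomial test is my assumption, because the protocol names no test.

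**1. Can N = 40 be reproduced from 25% versus 45%?** The normal-approximation formula is

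n = [(z_α·√(P0(1−P0)) + z_β·√(P1(1−P1))) / (P1−P0)]²

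- Two-sided 5%: [(1.960×0.4330 + 0.8416×0.4975)/0.20]² = (1.2674/0.20)² = 40.2. This is 41 when rounded up, so 40 is reproduced approximately.
- One-sided 5%: 32.0.
- Exact one-sided 5%: smallest n is 36, cut-off 14 (alpha 0.046, power 0.817).
- Exact one-sided 2.5%: smallest n is 46, cut-off 18 (alpha 0.024, power 0.828).

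So 40 comes close to 25%/45% only through the two-sided normal formula. None of these calculations gives the pair 40 and 18.

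**2. What does 18/40 deliver?** With X ~ Binomial(40, p), P(X ≥ 18) is:

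| True 6-month rate | P(X ≥ 18) | Meaning |
|---|---|---|
| 25% | 0.0047 | type I error at P0 |
| 31% | 0.0436 | type I error at the cited rate |
| 45% | 0.5609 | power at P1 |
| 50% | 0.7852 | |
| 50.4% | 0.80 | rate needed for 80% power |
| 51% | 0.8204 | |

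Type II error at 45% is 1 − 0.561 = 0.439. Against 25%, the rule uses about a tenth of the permitted alpha (0.0047 of 0.05).

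**3. Which hypotheses match 40 and 18?** Keep the 20-point gain but start from the cited rate, 31% versus 51%. The smallest exact one-sided 5% design with 80% power is n = 40, cut-off 18 (alpha 0.0436, power 0.820). A cut-off of 17 gives 0.083 at 31%, so 18 is the smallest cut-off that holds one-sided 5% there.

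**4. What would 45% against 31% need?** For 80% exact power, 76 patients at one-sided 5% (cut-off 31, alpha 0.045, power 0.803), or 95 at one-sided 2.5% (cut-off 39, alpha 0.024, power 0.809).

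**The case against.** The strongest reply is that 25% is a defensible null. The 31% figure pools all anaplastic gliomas, and section 10.3 says so. If it is a simple proportion of 125 patients (39/125, an assumed count), its exact 95% interval runs from 23% to 40% and includes 25%. The protocol's other evidence does not settle the direction. Section 4.2.4 reports "For 1p/19 there is a benefit in PFS from 50 to 157 months" against "Adding PCV to radiotherapy increases median PFS from 13 to 24 months" overall, and section 6.1 says that "oligodendrogliomas must present mutations in IDH1/2 as well as a co-deletion of chromosomes 1p/19q", which points to a better-prognosis group; but those are first-line data. Sections 4.1 and 4.5 describe short survival and low response rates after relapse. None of this is a 6-month PFS rate at relapse. I accept the reply: a reader might infer that 31% is the right null, and the documents do not establish that. What remains is the missing reason for 25%.

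A reader might also infer that a positive result would show only that palbociclib exceeds 25%. The printed rule does not support that. Section 10.3 has one criterion for benefit, 18/40, and its one-sided error at 31% is 0.044. Meeting it would reject 31% as well at one-sided 5%. At one-sided 2.5% it would not.

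Finally, the exact match in step 3 tempts one to conclude that the trial was designed for 31% versus 51% and that 25%/45% is a misprint. That is not proven. An N near 40 from the two-sided normal formula, with 18 taken as 45% of 40, would give the same printed figures.

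**Conclusion.** The inconsistency stands. P0 = 25%, P1 = 45%, beta read as 0.20, N = 40 and a cut-off of 18 cannot all describe one design: power at 45% is 56%, and 80% is reached only at a true rate of about 50%. Power at 45% depends on the cut-off and N, so it is 56% whichever null is used.

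The defect lies in the stated hypotheses and power. False-positive protection is adequate against both rates at one-sided 5%, at 0.005 and 0.044.

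The conclusion rests on two assumptions: the exact one-sided binomial calculation, and reading beta as 0.20. Taken literally, a beta of at least 0.20 is compatible with 0.44, but then it promises no minimum power at all.

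The point does not change how the printed result reads. The 6-month estimate in SAP section 1.2.1, 21.23% (95% CI 11 to 40.97), lies below both 25% and 31%, and its interval contains both. What is affected is the description of the design and the wording of any claim.

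**What to change.** Keep 40 patients and the 18/40 rule. In Protocol section 10.3:

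1. State which P0 and P1 the rule was derived from and by which calculation, with the reason for 25% in one sentence. If no record exists, say that P0, P1, beta and the cut-off do not reconcile and let item 2 describe the design.
2. Print the rule's actual properties, labelled as an exact one-sided binomial calculation added for description. Suggested text: At least 18 of 40 patients alive and progression-free at 6 months has type I error 0.005 at a true rate of 25% and 0.044 at 31%, and power 56% at 45% and about 80% at 50%.
3. Correct the beta line, whose inequality sets no minimum power.
4. State that the trial is not sized to show 45% against 31%.

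In SAP section 1.2.1, report the 6-month estimate and its interval against both 25% and 31%. Do not replace P0: the SAP already prints a database closure date and the 6-month estimate, so a new null would be chosen with the result in view.

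The cost is a few sentences and a less favourable stated power. No extra patients are needed.

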1.2. EFFICACY ANALYSES

1.2.1. PRIMARY EFFICACY ANALYSES: PFS

At 6 and 9 months the estimated PFS was 21.23% (with 95% CI 11-40.97), at 12 months it was 16.99% (with 95% CI 7.71-37.43) and from 18 to 48 months it was 11.32% (with 95% CI 3.68-34.86).

The median of PFS was 2.84 months (with 95% CI 2.71-5.39).

Table 22. PFS estimated survival ratio

Progression Free Survival	Events (% total N)	Patients at risk	% estimated cumulative survival ratio	CI 95%
At 6 months				
At 9 months				
At 12 months				
At 18 months				
At 24 months				
At 30 months				
At 36 months				
At 42 months				
At 48 months				

[figure not shown]
Note: Estimated using Kaplan-Meier product-limit method

Table 23. Median/mean PFS (estimated by Kaplan-Meier)

Progression Free Survival	Median (months)	CI 95%	Mean	CI 95%

Note: Estimated using Kaplan-Meier product-limit method

Figure 1. Progression Free Survival

In the 28 patients with PD, the median until progression was 2.8 months.

Table 24. Time until PD/exitus (only pts with event)

Overall	Overall (N=xx)
Time until PD/Exitus	
N	
Mean (95%CI)	
SD	
Median (95%CI)	
Range	

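### The 18/40 success rule does not fit its own design: against 25% its type I error is 0.005, and its power at 45% is 56%, although 40 patients fits a target of about 80%

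*Protocol*

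**What the plan says.** All the design inputs are in Protocol section 10.3.

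- **Historical basis.** "The 6-month progression-free survival (PFS-6m) was 31% for anaplastic gliomas". The section accepts that this series covers all anaplastic gliomas, not only anaplastic oligodendrogliomas.
- **Hypotheses.** The null is a rate of at most P0 and the alternative a rate of at least P1, with P0 = 25% and P1 = 45%, a gain of 20 points. The section does not explain why P0 is 25% when the cited rate is 31%.
- **Error rates.** The type I error is at most 0.05, with the number of sides not stated. The type II error is printed as a lower bound: "Type II error, $\beta \geq 0.20".
- **Size and rule.** "Sample size: 40 patients", and then "A benefit will be considered if 18/40 patients are alive and progression-free at 6 months". Neither the formula behind 40 nor the derivation of 18 is given.

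In the SAP text available, section 1.2.1 (primary efficacy analyses: PFS) gives survival estimates with 95% confidence intervals ("Note: Estimated using Kaplan-Meier product-limit method"). It has no null rate, test or cut-off.

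**The concern.** 18 is exactly 45% of 40, so the rule asks the observed rate to reach P1 itself. A cut-off placed at the alternative is met only a little more than half the time when the alternative is true, whatever error rates are written beside it. A critical value is normally placed between P0 and P1, just high enough to hold the type I error.

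This is the trial's only stated decision rule. A reader who sees 25% against 45%, 0.05 and 0.20 will take a result below 18/40 as coming from a trial with about 80% power. The rule does not have that power, so such a result carries less evidence against a 45% rate than the stated design implies.

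**Working it through.** **Inputs (Protocol 10.3).** n = 40, P0 = 0.25, P1 = 0.45, cited historical rate 0.31, rule: at least 18 successes. Assumption: the type II figure is a target of 0.20, that is, 80% power.

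**Step 1: reproduce the 40.** One-sample proportion, normal approximation:

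n = [(z_α·√(P0(1−P0)) + z_β·√(P1(1−P1))) / (P1 − P0)]²

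Here √(0.25 × 0.75) = 0.4330, √(0.45 × 0.55) = 0.4975, and z_β = 0.8416 for 80% power.

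- 0.025 per tail: [(1.960 × 0.4330 + 0.8416 × 0.4975) / 0.20]² = [(0.8487 + 0.4187) / 0.20]² = **40.2**
- One-sided 0.05: [(1.645 × 0.4330 + 0.4187) / 0.20]² = [(0.7122 + 0.4187) / 0.20]² = **32.0**

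The stated 40 matches 80% power at 0.025 per tail.

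**Step 2: properties of each cut-off.** Exact binomial, P(X ≥ r | n = 40, p):

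| Cut-off | p = 25% (type I) | p = 31% | p = 45% (power) | Type II error |
|---|---|---|---|---|
| 15/40 | 0.0544 | 0.2333 | 0.8674 | 0.133 |
| 16/40 | 0.0262 | 0.1450 | 0.7858 | 0.214 |
| 17/40 | 0.0116 | 0.0830 | 0.6815 | 0.319 |
| **18/40** | **0.0047** | **0.0436** | **0.5609** | **0.439** |

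**Step 3: read the table.**

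- With P0 = 25%, the lowest valid cut-off is 16 at one-sided 0.05 and 17 at 0.025. Against these, 18 loses 78.6 − 56.1 = 22 points of power, or 68.1 − 56.1 = 12 points.
- Solving P(X ≥ 18 | 40, p) = 0.80 gives p = 0.504. The rule has 80% power only for a true rate of about 50%.
- At 31%, 18 is the smallest cut-off with type I error at or below 0.05; 17 gives 0.083. That is a second possible origin for 18, but it would mean the null tested is not the stated 25%, and power at 45% is still 56%.
- Reading the rule as more than 18 makes it stricter: type I error 0.0017, power 43.5%.

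**Step 4: can n = 40 meet both limits?** No. 15 breaks the 0.05 limit and 16 has a type II error of 0.214. Exact designs that meet one-sided 0.05 and 80% power include 14/36 (0.0461; 81.7%) and 16/41 (0.0333; 82.3%). At 0.025, the smallest is 18/46 (0.0242; 82.8%).

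**The case against.** **The printed limits are literally met.** A type I error of 0.0047 is below 0.05 and a type II error of 0.439 is above 0.20. That is true, and reading 0.20 as a target is an inference. But a lower bound on the type II error constrains nothing, since a trial with no power would satisfy it, and the stated 40 reproduces at 80% power. The reading is well supported, and the protocol nowhere discloses 56% power.

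**The size of the shortfall depends on sidedness.** This stands. On the convention that reproduces 40 (0.025 per tail), the valid cut-off is 17, so the cut-off costs 12 points; the remaining gap from 68.1% to 80% comes from the sample size, because the exact test needs 46. The 22-point figure belongs to one-sided 0.05. Neither convention leads to 18.

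**The error is conservative and will not change this trial's answer.** This largely stands. The SAP reports the database closed on 10-10-2019 and prints a 6-month PFS estimate of 21.23% (95% CI 11 to 40.97), below 25% and below every cut-off considered here. SAP tables also use a denominator of 34, to which neither 16/40 nor 18/40 applies directly. These facts limit the practical effect. They do not give the rule the properties stated for it.

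**The 31% link may be coincidence.** It may be; 45% of 40 is the simpler explanation. Either way, the protocol must say which null rate the cut-off tests.

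**Conclusion.** The concern holds. As written, 18/40 has a type I error of 0.0047 at 25% and power of 56.1% at 45%, so its type II error is 0.44 against the 0.20 given. These are exact binomial results and need only n = 40, the two stated rates and the rule read as at least 18. Calling the gap a departure from the design also assumes that 0.20 was a target and that its inequality sign is a slip, possibly from translation.

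The sample size is not the main fault. The Kaplan-Meier estimate and its interval remain interpretable. What has to be corrected is the claim that the decision rule carries the stated error rates.

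**What to change.** In Protocol section 10.3, state the sidedness, the null rate that the cut-off tests and how it relates to the cited 31%. Check the inequality on the type II error against the source-language text. Then choose one of the following.

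- **Keep 18/40 and disclose its properties (preferred at this stage):** type I error 0.005 at 25% and 0.044 at 31%; power 56% at 45%; 80% power only near a true rate of 50%. This needs a few lines and no patients, and the cut-off does not move.
- **Change the cut-off to 16/40**, if 25% and one-sided 0.05 were meant: type I error 0.026, power 78.6%, type II error 0.21, which must not be described as at most 0.20. The cost is a false-positive probability of 14.5%, instead of 4.4%, if the true null rate is 31%. Because the SAP already prints a 6-month estimate, the change would have to be labelled post hoc. If both limits had to hold exactly, the sample size would also have to differ (14/36 or 16/41), which is of little use after database closure.

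In either case, add the chosen rule to SAP section 1.2.1 and say how a rule written over 40 patients is applied to the 34 in the SAP tables.
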